2.3 Enrolled Not Dispensed

Enrolled Not Dispensed is a subset of All Enrolled subjects/eyes that have not been exposed to study lenses. Lenses from the trial fitting set used only for fit, power, and/or VA determination are not considered study lenses in this context.

2.4 Completed

The Completed analysis set consists of Enrolled Dispensed subjects/eyes completing the study.

2.5 Discontinued

The Discontinued analysis set consists of Enrolled Dispensed subjects/eyes not completing the study.

3 Subject Characteristics and Study Conduct Summaries

Demographic information (age, sex, ethnicity, and race), recent lens wearing experience (wear modality, wear success), and habitual lens information will be presented by lens group and overall for the All Enrolled analysis set.

Baseline data will be summarized by lens group, for Completed and Discontinued analysis sets separately, as applicable.

The following tables and listings for study conduct summaries will be presented:

- Accountability by Eyes Enrolled in the Study and Distribution by Status
- Listing of Lens Assignment by Investigator
- Discontinued Subjects Tabulated by Completed Visits and Reason for Discontinuation with Incidence Rates
- Listing of Subjects Discontinued from Study
- Listing of Out-of-Window Visits

4 Effectiveness Analysis Strategy

This study defines one primary effectiveness endpoint [REDACTED]

[REDACTED] Unless otherwise specified, separate summary tables will be presented for the Completed and the Discontinued analysis sets with the following distinction:

- Completed Control (eyes/subjects)
- Completed Test (eyes/subjects)

- Discontinued Control (eyes/subjects)
- Discontinued Test (eyes/subjects)

No inferential testing will be performed on the effectiveness endpoints, and format of the reporting tables will reference FDA’s 510(k) guidance document (Clinical Appendix C, Summary of Reporting Tables; Clinical Appendix D, Trend Analysis Profile) as well as ISO 11980:2012 (Appendix A.3, Reporting of Results).

4.1 Effectiveness Endpoints

Primary Endpoint

The primary endpoint is distance VA with study lenses, collected in Snellen, for each eye. Conversion will be made to the logMAR scale.

[REDACTED]

[REDACTED]

- [REDACTED]
- [REDACTED]
- [REDACTED]
- [REDACTED]
- [REDACTED]
- [REDACTED]
- [REDACTED]
- [REDACTED]
- [REDACTED]
- [REDACTED]
- [REDACTED]
- [REDACTED]

4.2 Effectiveness Hypotheses

Primary Effectiveness

No inferences are to be made on the primary effectiveness endpoint; therefore, no hypotheses are formulated.

[REDACTED]

[REDACTED]

4.3 Statistical Methods for Effectiveness Analyses

4.3.1 Primary Effectiveness Analyses

Summary statistics will be provided at each visit (Dispense, Week 1, Week 2, Month 1, Month 2, Month 3, and all unscheduled visits combined). Counts and percentages on the Snellen categories will be displayed, and descriptive statistics (number of observations, mean, standard deviation, median, minimum, and maximum) for the converted logMAR values will be provided.

[REDACTED]

- [REDACTED]

- [REDACTED]

- [REDACTED]

[REDACTED]

[REDACTED]

- [REDACTED]

- [REDACTED]

- [REDACTED]

- [REDACTED]

[REDACTED]

[REDACTED]

[REDACTED]

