10.4 Unscheduled Visits

If a subject visit occurs between any regularly scheduled visits, this visit must be documented as an Unscheduled Visit or Early Exit as applicable. During all unscheduled visits, the Investigator must conduct the following procedures, as appropriate:

- Collect AE information, as applicable
- Record changes in medical condition or concomitant medication, as applicable
- Collect device deficiency information, as applicable
- VA with habitual correction
- Manifest refraction
- BCVA with manifest refraction

[REDACTED]

- Perform biomicroscopy (assessments with or without lenses, as applicable)
- VA with study lenses

- [REDACTED]
- [REDACTED]
- [REDACTED]
- [REDACTED]

The Investigator may perform additional procedures for proper diagnosis and treatment of the subject according to Table 3–1. The Investigator must document this information in the subject’s case history source documents.

If, during an Unscheduled Visit, the subject is to discontinue IP or is discontinuing from the study, the Investigator must conduct Exit procedures according to Table 3–1, as possible. Do not complete an Unscheduled Visit if a subject is exiting between scheduled study visits. An Early Exit assessment should be completed instead.

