10.5.2 Discontinuations

Discontinued subjects are individuals who voluntarily withdraw or are withdrawn from the study by the Investigator after signing the informed consent.

Subject numbers of discontinued subjects must not be re-used.

Subjects may discontinue from study or study treatment at any time for any reason. Subjects may also be discontinued from study treatment at any time if, in the opinion of the Investigator, continued treatment poses a risk to their health.

For subjects discontinuing from the study, the Investigator must complete all Exit procedures according to Table 3–1, if the subject is willing and able, and if in the opinion of the Investigator it is safe for the subject to do so.

The Investigator must document the reason for study or treatment discontinuation in the subject’s case history source documents.

To ensure the safety of all subjects who discontinue early, Investigators must assess each subject and, if necessary, advise them of any therapies and/or medical procedures that may be needed to maintain their health.

10.5.3 Schedule of Procedures and Assessments for Subjects Discontinued from Investigational Product

Other than screen failures, if a subject discontinues from the study, the subject should undergo an Early Exit Visit. Refer to Table 3–1.

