1.2 Study Description

Key components of the study are summarized in Table 1-1.

Table 1-1 Study Description Summary

Study Design	Prospective, multi-center, randomized, [REDACTED] controlled, double-masked, parallel-group
Study Population	
Volunteer subjects aged 18 or over who are adapted daily wear frequent replacement soft contact lens wearers, excluding Biofinity habitual wearers, have at least 3 months of soft contact lens wearing experience, and who wear their habitual lenses at least 5 days per week and at least 8 hours per day.
 
Subjects must require contact lens correction in a sphere power range from -1.00 to -6.00 D. [REDACTED] [REDACTED] [REDACTED]
 
Target to complete: 90 subjects (60:30; Test:Control) Planned to enroll: ~120 subjects

Number of Sites	~8 (US)
Test Product	[REDACTED] soft contact lenses [REDACTED]
Control Product	CooperVision® BIOFINITY® (comfilcon A) soft contact lenses (Biofinity)
Duration of Treatment	Approximately 3 months
Visits	
Visit 1: Screening/Baseline/Dispense (Day 1) Visit 2: Week 1 Follow-up (Day 8 -2/+2 days) Visit 3: Week 2 Follow-up (Day 15 -3/+3 days) Visit 4: Month 1 Follow-up (Day 30 -3/+5 days) Visit 5: Month 2 Follow-up (Day 60 -3/+5 days) Visit 6: Month 3 Follow-up/Exit (Day 95 -3/+5 days)

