5.3.2 Biomicroscopy Findings/Slit Lamp Examination

Biomicroscopy assessment will be performed at all study visits, including Visit 1 to 6 and unscheduled visits. The reporting unit for each biomicroscopy finding will be *eye*.

A summary of grade category counts and percentages will be presented for each parameter at each scheduled visit and all unscheduled visits combined. A listing of "Other" slit lamp findings will also be provided.

Additionally, for each biomicroscopy parameter, counts and percentages of eyes that experience an increase of ≥ 2 grades from baseline (Visit 1) to any subsequent visit will be presented, together with a supportive listing.

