VA w/ habitual correction (OD,OS Snellen distance)	X					X	X	(X)
Manifest refraction ⁴	X	(X)	(X)	(X)	(X)	X	X	(X)
BCVA ⁴ (OD,OS Snellen distance with manifest refraction)	X	(X)	(X)	(X)	(X)	X	X	(X)
	■					■	■	■
Biomicroscopy	X	X	X	X	X	X	X	(X)
	■							

Printed By:

Print Date:

Procedure/ Assessment	Visit 1 Screening/ Baseline/ Dispense	Visit 2 Week 1 Follow-up ⁵	Visit 3 Week 2 Follow-up ⁵	Visit 4 Month 1 Follow-up ⁵	Visit 5 Month 2 Follow-up ⁵	Visit 6 Month 3 Follow-up/Exit ⁵	Early Exit	USV
	Day 1	Day 8 (-2/+2 days)	Day 15 (-3/+3 days)	Day 30 (-3/+5 days)	Day 60 (-3/+5 days)	Day 95 (-3/+5 days)		
Randomize and record lens power	X							
[REDACTED]	■							
Order study lenses*	X							
IP Dispense*	X	X	(X)	(X)	(X)			(X)
VA w/ study lenses (OD, OS Snellen distance) ¹	X	X	X	X	X	X	X	(X)
[REDACTED]		■	■	■	■	■	■	■
[REDACTED]	■	■	■	■	■	■	■	■
[REDACTED]	■	■	■	■	■	■	■	■
[REDACTED]	■	■	■	■	■	■	■	■
[REDACTED]		■	■	■	■	■	■	■

Printed By:

Print Date:

Procedure/ Assessment	Visit 1 Screening/ Baseline/ Dispense	Visit 2 Week 1 Follow-up ⁵	Visit 3 Week 2 Follow-up ⁵	Visit 4 Month 1 Follow-up ⁵	Visit 5 Month 2 Follow-up ⁵	Visit 6 Month 3 Follow- up/Exit ⁵	Early Exit	USV
	Day 1	Day 8 (-2/+2 days)	Day 15 (-3/+3 days)	Day 30 (-3/+5 days)	Day 60 (-3/+5 days)	Day 95 (-3/+5 days)		
[REDACTED]	■	■	■	■	■	■	■	■
[REDACTED]	■	■	■	■	■	■	■	■
[REDACTED]	■	■	■	■	■	■	■	■
[REDACTED]	■	■	■	■	■	■	■	■
[REDACTED]	■	■	■	■	■	■	■	■
AEs	X	X	X	X	X	X	X	(X)
Device deficiencies	X	X	X	X	X	X	X	(X)
Exit Form	(X)	(X)	(X)	(X)	(X)	(X)	X	(X)

USV = Unscheduled Visit
 *source only

[REDACTED]

⁵All follow-up visits should be scheduled at least 4 hours after lens insertion.

[REDACTED]

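### Do the Discontinued-set tables lose the Early Exit visual acuity and biomicroscopy records?

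*SAP*

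**What the plan says.** The primary endpoint is distance VA with study lenses, reported descriptively. SAP 4.3.1 fixes the reporting times: "Summary statistics will be provided at each visit (Dispense, Week 1, Week 2, Month 1, Month 2, Month 3, and all unscheduled visits combined". For slit-lamp grades, SAP 5.3.2 says: "A summary of grade category counts and percentages will be presented for each parameter at each scheduled visit and all unscheduled visits combined". Neither sentence mentions Early Exit.

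The schedule (Protocol Table 3-1, repeated as SAP Table 11-1) gives Early Exit its own column beside the one for unscheduled visits. The row "VA w/ study lenses (OD, OS Snellen distance") is marked as required at Early Exit and as conditional at unscheduled visits, and so is biomicroscopy. Protocol 10.5.3 states: "Other than screen failures, if a subject discontinues from the study, the subject should undergo an Early Exit Visit". Protocol 10.4 tells the site how to record an exit that falls between visits: "Do not complete an Unscheduled Visit if a subject is exiting between scheduled study visits. An Early Exit assessment should be completed instead".

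These subjects are tabulated on their own. SAP 2.5 reads: "The Discontinued analysis set consists of Enrolled Dispensed subjects/eyes not completing the study". SAP sections 4 and 5 call for separate Completed and Discontinued tables by lens.

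Two further statements matter. Protocol 12.5 says every value obtained from evaluable subjects or eyes is used, without imputation. SAP 5.3.2 also counts eyes whose grade rises by 2 or more from baseline "to any subsequent visit will be presented, together with a supportive listing".

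**The concern.** Set side by side, these sections seem to leave a hole. An exit between scheduled visits is not one of the six named visits, and Protocol 10.4 tells the site not to enter it as an unscheduled one. A programmer who follows the visible lists word for word would have no row for it.

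The gap would fall where it is least welcome. The reading taken at exit is the closest in time to the decision to stop, and it would drop out of the tables that describe those who stopped. No inferential testing is planned, so the descriptive tables are the effectiveness result. Biomicroscopy has a second route into the report through the table of grade increases. VA has no such route in the text that can be read. A subject who left before Week 1 would appear with dispense-day VA only.

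**Working it through.** The plan states no figure on this point, so there is none to reproduce. The check has three parts.

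**1. Where an Early Exit record could go**

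| Source | What it settles |
|---|---|
| SAP 4.3.1 and 5.3.2 | Scheduled visits and pooled unscheduled visits; Early Exit not named |
| Protocol 10.4 | Which visit type the site completes at data capture |
| Protocol 12.5 | Collected data from evaluable subjects and eyes are used |
| SAP 5.3.2, opening sentence | Describes the set of study visits as Visits 1 to 6 plus unscheduled visits |
| Rest of SAP 4.3.1; Protocol 12.4.1.2; SAP section with Table 7-1 | Redacted |

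Protocol 10.4 governs data capture and does not define table rows. SAP 5.3.2 names only two kinds of visit although the schedule requires biomicroscopy at Early Exit. That suggests, without proving it, that the SAP counts Early Exit among the visits outside the schedule. Table 7-1 is visible only by its title, Expanded Window. A windowing table is where one would expect a rule that assigns an exit record to a nominal visit.

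**2. How much data is involved**

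The documents give no discontinuation rate. SAP Table 1-1 gives about 120 to enroll and "Target to complete: 90 subjects (60:30; Test:Control"). The gap is 120 − 90 = 30 subjects, or 30/120 = 25%. At 2:1 this is 20 test and 10 control. It is a planning gap and not a bound on dropout. The 90 is a target, and enrolled means consented, so some of the 30 may be screen failures who never enter the Discontinued set.

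The protocol windows for Visits 2 to 5 are Days 6–10, 12–18, 27–35 and 57–65, that is 5 + 7 + 9 + 9 = 30 days. Between Day 2 and Day 91 there are 90 days, so 90 − 30 = 60 days (60/90 = 67%) lie outside every window. If exits were spread evenly (an assumption):

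| Discontinued subjects (assumed) | Exits outside a window at 67% | Range as that share goes from 0% to 100% |
|---|---|---|
| 30 | 20 | 0 to 30 |
| 15 | 10 | 0 to 15 |
| 6 | 4 | 0 to 6 |

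The 67% rests on the protocol windows. Wider analysis windows, which the title of Table 7-1 implies, would lower it.

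For one exiting eye with *k* scheduled visits attended, Dispense included, and no unscheduled visit, there are (*k* − 1) + 1 = *k* VA values after dispensing. Early Exit is 1 of them: 1/1 = 100% for an exit before Week 1, 1/2 = 50% before Week 2, 1/5 = 20% before Month 3. This is the share for each eye and says nothing about how many eyes are affected.

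**3. What depends on the choice of row**

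- Completed tables: nothing, because these subjects have no Early Exit record.
- Exits made at a scheduled visit: nothing. The Exit Form is provided for at every scheduled visit, and the data sit in that visit's row.
- Increases of 2 or more grades: nothing, since the wording covers any later visit and a listing supports it.
- Adverse events and device deficiencies: nothing, because neither summary uses the visit list. Protocol 11.2 also makes a clinically relevant worsening of a protocol parameter an adverse event.
- Discontinued VA and grade-by-visit tables: only the row in which the exit reading appears, provided Protocol 12.5 is followed.

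**The case for a change.** The best case for a change is that it costs a phrase in each of two SAP sections and removes any doubt. SAP 5.3.2 carries no redaction mark and no cross-reference to a windowing rule, so for biomicroscopy the silence is in plain sight. Two competent programmers could place the same record differently, one in the pooled unscheduled row and one in a windowed visit. For VA, no table that can be read serves as a backstop.

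Part of this stands. The visible lists do not name Early Exit, and the protocol does keep it apart from an Unscheduled Visit. Naming the row would be tidy.

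What does not stand is the step from unnamed to left out. Dropping the records would breach Protocol 12.5, so the literal reading is the one an analyst should reject. The missing VA backstop cannot be held against the plan either, because the text that follows the VA paragraph in SAP 4.3.1 is blacked out. What is left is a choice of display between rows that all show the data, in tables with no test and no success criterion.

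**Conclusion.** No change is needed. The visible visit lists are silent on Early Exit, but an omission cannot be shown, since the sections most likely to hold a mapping rule are redacted and Protocol 12.5 points to the records being used. The remaining gap is one of table layout, which an analyst would settle sensibly by giving the exit its own row, mapping it to a visit by window, or pooling it with unscheduled visits.

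The effect is confined to the Discontinued-set VA and grade-by-visit tables. Its size cannot be fixed from the documents. The counts above rest on assumed numbers of discontinuations and evenly spread exits, and a wider analysis window would reduce them. The Completed tables, the safety summaries that do not depend on the visit list and the descriptive conclusion are unaffected. This rests on two assumptions: that Protocol 12.5 is applied as written, and that the redacted text does not exclude Early Exit data.

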4.4 Multiplicity Strategy

No multiplicity adjustment needs to be considered for the effectiveness endpoints since no formal hypothesis testing will be conducted.

4.5 Subgroup Analyses and Effect of Baseline Factors

It is not expected that demographic or baseline characteristics will have an impact on the study results in this study. No subgroup analyses are planned.

4.6 Interim Analysis for Effectiveness

No interim analysis is planned for effectiveness endpoints.

5 Safety Analysis Strategy

Unless otherwise specified, separate summary tables will be presented for the Completed and the Discontinued analysis sets with the following distinction:

- Completed Control (eyes/subjects)
- Completed Test (eyes/subjects)
- Discontinued Control (eyes/subjects)
- Discontinued Test (eyes/subjects)

Subjects/eyes will be categorized under the actual lens exposed.

5.1 Safety Endpoints

The safety endpoints include the following:

- Adverse events (AE)
- Biomicroscopy Findings/Slit Lamp Examination
 - Limbal hyperemia

- Bulbar hyperemia
 - Corneal staining
 - Conjunctival staining
 - Palpebral conjunctival observations
 - Corneal epithelial edema
 - Corneal stromal edema
 - Corneal vascularization
 - Conjunctival compression/indentation
 - Chemosis
 - Corneal infiltrates
 - Other findings
- Device deficiencies

5.2 Safety Hypotheses

There are no formal safety hypotheses in this study. The focus of the safety analysis will be a comprehensive descriptive assessment of safety endpoints listed in Section 5.1.

5.3 Statistical Methods for Safety Analyses

5.3.1 Adverse Events

The applicable definition of an AE is in the study protocol. All AEs occurring from when a subject signs informed consent to when a subject exits the study will be accounted for in the reporting. Analysis and presentation of pre-treatment AEs will be separated from treatment-emergent AEs occurring during the study period. A pre-treatment AE is an event that occurs after signing informed consent but prior to exposure to the study lens (not including trial fitting lenses). The period for treatment-emergent AE analysis starts from exposure to study lens until the subject completes or is discontinued from the study.

Descriptive summaries (counts and percentages) for ocular and nonocular AEs will be presented by Medical Dictionary for Regulatory Activities (MedDRA) Preferred Terms (PT). Serious AEs and significant non-serious ocular AEs will be noted. Additionally, relationship to lens will be identified in all AE tables. Unit of presentation for ocular AEs will be eye and nonocular AEs will be subject.

Individual subject listings will be provided for both pre-treatment and treatment-emergent AEs, where any AE leading to study discontinuation will be indicated.

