3 PROTOCOL SUMMARY

This will be a prospective, randomized, [REDACTED] controlled, double-masked, parallel-group daily wear clinical study.

Approximately 8 sites in the US will enroll approximately 120 subjects. Subjects will be expected to attend 6 office visits: Screening/Baseline/Dispense, Week 1 Follow-up, Week 2 Follow-up, Month 1 Follow-up, Month 2 Follow-up, and Month 3 Follow-up/Exit. The total expected duration of participation for each subject is approximately 3 months in this daily wear clinical study. Approximately 80 subjects will be assigned to wear the test lenses and 40 subjects will be assigned to wear the control lenses, following the 2:1 subject allocation ratio as recommended by ISO 11980:2012 and the US FDA 510(k) guidance document.

Subjects and the study personnel conducting the study evaluations will be masked to treatment. Subjects who meet the inclusion and exclusion criteria will be randomized to wear either the test contact lenses [REDACTED] in both eyes or the control contact lenses (Biofinity) in both eyes for 3 months of daily wear exposure. Following randomization, subjects will be trial fit in the assigned study lens using the fitting set supplied by the Sponsor, and the overall fit and correct contact lens power for each eye will be determined. [REDACTED]

[REDACTED]
[REDACTED]
[REDACTED]
[REDACTED]

The delegated [REDACTED] staff member will then complete a contact lens order form to obtain lenses for each subject. The Sponsor will send investigational products for each subject to the site after receiving an order from the Investigator.

At the Screening/Baseline/Dispense Visit, study lenses will be dispensed to qualified subjects and the subject will be provided with sufficient lens supplies to follow a monthly replacement schedule until the next visit. All study lenses will be worn for at least 5 days per week and 8 hours per day in a daily wear modality (eg, will not be worn while sleeping). [REDACTED]

[REDACTED]
[REDACTED]

Problem lenses (if any) will not be discarded, but collected by the subject and returned to the investigational site. Regardless of whether the subject is randomized to the test or the control group, CLEAR CARE® Cleaning & Disinfecting Solution (CLEAR CARE) must be used for cleaning and disinfection. [REDACTED]

[REDACTED]
[REDACTED]

[Redacted]

[Redacted]

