7 INVESTIGATIONAL PLAN

7.1 Study Design

This will be a prospective, randomized, [REDACTED] controlled, double-masked, parallel-group, daily wear clinical study.

This clinical study will engage approximately 8 clinic sites to enroll approximately 120 subjects with approximately 15 subjects per site.

[figure not shown]
Subjects will be expected to attend 6 office visits: Screening/Baseline/Dispense, Week 1 Follow-up, Week 2 Follow-up, Month 1 Follow-up, Month 2 Follow-up, and Month 3 Follow-up/Exit. The total expected duration of participation for each subject is approximately 14 weeks with approximately 3 months of exposure to study lenses in this daily wear study. Subjects will be randomized to wear either the test [REDACTED] contact lenses in both eyes or the control Biofinity contact lenses in both eyes.

Following randomization, study lenses will be dispensed to the subject. Subjects will be provided with sufficient lens supplies to follow a monthly replacement schedule until the next scheduled visit.

Subjects will wear the lenses while awake in a daily wear modality. CLEAR CARE will be used for daily cleaning and disinfection. [REDACTED]

The estimated time to recruit subjects for this study is approximately 6 weeks. The study is expected to take approximately 14 weeks for completion from the last patient first visit. The study outline is provided below:

Figure 7-1 Flowchart of Study Visits

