1.3 Randomization

A member of the Randomization Programming group at Alcon who is not part of the study team will generate the randomized allocation schedule(s) for study lens assignment.

[REDACTED]

Subjects will be randomized in a 2:1 ratio to receive either [REDACTED] or Biofinity contact lenses, respectively. [REDACTED]

[REDACTED]

[REDACTED]

Randomization schedule will be blocked to ensure a balance (2:1) in lens allocation within sites.

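### Ocular adverse events are tabulated by eye, with no readable table of subjects affected, although the lens is randomized to the subject and worn in both eyes

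*SAP*

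**What the plan says.** **Unit of assignment and exposure.** SAP 1.3 assigns lenses to people: "Subjects will be randomized in a 2:1 ratio to receive either" one lens or the other. Protocol 7.1 has each subject wear the assigned "contact lenses in both eyes or the control Biofinity contact lenses in both eyes". Both eyes of a subject therefore always carry the same product.

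**Unit of the safety tables.** SAP 5.3.1 states: "Unit of presentation for ocular AEs will be eye and nonocular AEs will be subject". The statistics are simple: "Descriptive summaries (counts and percentages) for ocular and nonocular AEs will be presented by Medical Dictionary for Regulatory Activities" Preferred Term. Serious and significant non-serious ocular events are noted, and relationship to the lens is identified. SAP 5.3.2 continues the rule for slit-lamp findings: "The reporting unit for each biomicroscopy finding will be" eye. The table of increases of 2 or more grades from baseline is also counted in eyes.

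**What exists by subject.** SAP 5.3.1 adds listings: "Individual subject listings will be provided for both pre-treatment and treatment-emergent AEs". SAP 5.3.2 adds a supporting listing for the grade increases. SAP 3 tabulates discontinued subjects by reason. Protocol 12.6 names no unit and adds no subject-level ocular table.

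**Sets and purpose.** By default, SAP 5 splits the safety tables into Completed and Discontinued, each by lens. SAP 5.2 and Protocol 12.6 make the safety analysis descriptive, without hypotheses.

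**The concern.** Because safety is assessed by description alone, the tables are the comparison with the predicate lens. A natural question of them is how many people on each lens had an ocular event. The eye percentage does not answer it, because it depends on two things: how many subjects were affected, and in how many of those both eyes were affected. Two lenses with the same eye percentage may differ in the proportion of subjects affected, and a reader of the tables could not see it.

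The plan already uses the subject for nonocular events, and it justifies its size in subjects (Protocol 12.8, SAP 8). The subject count is missing for the organ that wears the device. What is at stake is how clearly the ocular safety comparison reads in the unit that was randomized.

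**Working it through.** **Inputs**
- Planned assignment (Protocol 3): "Approximately 80 subjects will be assigned to wear the test lenses and 40 subjects will be assigned to wear the control lenses".
- Target completers (SAP Table 1-1): 60 Test and 30 Control, 90 in all.
- Eyes per subject on the assigned lens: 2 (Protocol 7.1).
- Share b of affected subjects with both eyes affected: not given. Assumption: anywhere from 0 to 1.
- Counting assumptions: an eye counts once per table row, and both eyes of a subject fall in the same analysis set.

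**The plan's own figures.** At 2:1, 120 × 2/3 = 80 and 120 × 1/3 = 40. For completers, 90 × 2/3 = 60 and 90 × 1/3 = 30. Both agree with the documents. Since the safety tables are split by completion, the completer denominators are the relevant ones: 60 × 2 = 120 Test eyes and 30 × 2 = 60 Control eyes.

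**Bounds.** If x of 2n eyes are affected, the number of affected subjects lies between x/2 rounded up (all bilateral) and the smaller of x and n (all unilateral). At an illustrative 10% of eyes:

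| Completed set | Eyes affected | Subjects affected | Share of subjects |
|---|---|---|---|
| Test | 12/120 = 10% | 6 to 12 of 60 | 10% to 20% |
| Control | 6/60 = 10% | 3 to 6 of 30 | 10% to 20% |

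If one arm is all unilateral and the other all bilateral, the comparison is 20% against 10% of subjects, a ratio of 2.0.

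**Between the extremes.** Each affected subject contributes 1 + b eyes on average, so eye share = subject share × (1 + b)/2. Hence subject share = 2 × eye share/(1 + b). At equal eye shares, the ratio of subject shares, Test to Control, is (1 + b Control)/(1 + b Test). At 10% of eyes in both arms, as rates and ignoring rounding to whole subjects:

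| b Test | b Control | Test subjects | Control subjects | Ratio |
|---|---|---|---|---|
| 0 | 1 | 0.20/1.0 = 20.0% | 0.20/2.0 = 10.0% | 2.0 |
| 0.2 | 0.8 | 0.20/1.2 = 16.7% | 0.20/1.8 = 11.1% | 1.5 |
| 0.3 | 0.6 | 0.20/1.3 = 15.4% | 0.20/1.6 = 12.5% | 1.23 |
| 0.5 | 0.5 | 0.20/1.5 = 13.3% | 0.20/1.5 = 13.3% | 1.0 |

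**Where twofold is not reached.** Above 50% of eyes, the all-unilateral pattern is no longer possible. The maximum falls to 1.67 at 60% (100%/60%) and 1.33 at 75% (100%/75%). Odd counts in small sets also matter. At 5% of eyes, Control has 3/60 eyes, which must be 2 or 3 of 30 subjects (6.7% to 10%). If the 6/120 Test eyes are all unilateral, Test has 6/60 = 10% of subjects, and the largest ratio in that direction is 10%/6.7% = 1.5.

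**The case against.** The best case for leaving the plan alone has five parts.

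- **The information is not lost.** Subject listings are planned for AEs and for grade increases. With about 120 subjects, affected people can be counted. This stands, but the count would have to be repeated by Preferred Term, lens and analysis set, which is the job of a summary table.
- **The extreme is unlikely.** Nothing in the documents suggests that bilaterality differs by lens. With equal bilaterality, eye and subject percentages rank the lenses alike. This stands: twofold is a ceiling, not a forecast.
- **Per-eye reporting is natural.** Slit-lamp grades belong to eyes. This stands, and the eye tables should remain. The plan's explicit references to FDA and ISO table formats are in the effectiveness sections (Protocol 12.4, SAP 4), so they do not settle the safety format. Adding a column displaces nothing in any case.
- **The headings in SAP 5 carry an eyes/subjects label.** This is weak: the label is generic, and 5.3.1 then fixes the eye for ocular events.
- **Text is blacked out between SAP 5.3.3 and Section 8.** A subject-level table could be there. No readable text points to one, but the point is limited to what can be read.

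A reader might also infer that eye denominators make the safety database look twice as large. With zero events, 60 subjects give a one-sided 95% upper limit of 1 − 0.05^(1/60) = 4.9%, whereas 120 eyes taken as independent give 1 − 0.05^(1/120) = 2.5%. The documents do not support that as a criticism of the plan. No readable text plans a safety confidence interval, the SAP nowhere treats eyes as independent, and enrolment, the completion target and the guidance minimums are all stated in subjects.

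**Conclusion.** The gap is real and modest. In the readable text, ocular events and grade increases are tabulated by eye, and the number of subjects affected is not tabulated. At equal eye percentages, the subject percentages can differ by at most a factor of two, by less at intermediate bilaterality, and not at all when bilaterality is equal. The result rests on the target of 60 and 30 completers, an illustrative 10% of eyes, and an assumed bilateral share over its whole range.

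Two further inferences go too far. One is that a test or decision is compromised: none is planned for safety, and the SAP's executive summary states that success criteria do not apply. The other is that the missing figure is the share of subjects harmed by a lens. The protocol counts AEs regardless of causality, so the figure is subjects with an event. The point is a cheap improvement to descriptive reporting.

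**What to change.** Keep every eye table. In SAP 5.3.1, add to each ocular AE row (any ocular AE, each Preferred Term, serious, significant non-serious, lens-related) the number and percentage of subjects with at least one event in either eye. Give these by lens within the Completed and Discontinued sets, with subjects as the denominator. In SAP 5.3.2, the same either-eye subject count could optionally be added to the table of increases of 2 or more grades. If the blacked-out text already holds such a table, a cross-reference from 5.3.1 is enough.

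The cost is a few lines of SAP wording and one added column, from data already collected. The tables become slightly longer. Because 2/(1 + b) is never below 1, the subject percentages will equal or exceed the eye percentages, so the two denominators need clear labels.
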